8.3 STATISTICAL ANALYSES

Descriptive statistics will be computed for all variables together with 95% CI whenever relevant and applicable. Associations between qualitative-independent variables will be tested using χ^2 test. Comparisons between two or more independent groups regarding a quantitative variable are to be conducted using analysis of variance (ANOVA) or Kruskal-Wallis non-parametric test, if normality assumption is not met. ANCOVA may also be used to adjust for potential confounding factors. Associations between quantitative independent variables will be analysed using Pearson's or Spearman's correlation coefficient depending on normality assumption. All tests will be two-sided, considering a significance level of 0.05.

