1 PROTOCOL SUMMARY

1.1 SYNOPSIS

Title:	Deprescribing: a portrait and out-comes of the reduction of Polypharmacy in Portugal (DePil17-20)
Study Description:	This study protocol comprises three phases. The first two phases will be nationwide and aim to evaluate the prevalence and patterns of polypharmacy and assess the barriers and facilitators of deprescribing perceived by older adults, as well as their willingness to be deprescribed and to self-medicate. The third and last phase will be a non-pharmacological randomised clinical study to measure the impact of enablement of older adults in their willingness to be deprescribed and related quality of life.
Objectives:	Primary Objective: Willingness to be deprescribed after the intervention Secondary Objectives: Quality of life after the intervention
Study Population:	Older adults (≥ 65 years) in Portugal
Description of Study	In the intervention group the investigators will give enablement tools and talks with their General Practitioners about how to issue the problem of polypharmacy.
Intervention:	
Study Duration:	36 months.
Participant Duration:	6 month.

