3 OBJECTIVES AND ENDPOINTS

Primary objective is to assess the enablement of older adults while being Deprescribed in the rise of Willingness to be Deprescribed.

Secondary objective is to assess the enablement of older adults while being Deprescribed in the rise of their Quality of Life outcome.

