Two groups will be created with a minimum of 190 patients each, one of which will be composed from patients from the region of Aveiro, Coimbra and Guarda and the other from patients from the region of Castelo Branco, Leiria and Viseu. In the intervention group we will give enablement tools and talks with their GPs about how to issue the problem of polypharmacy. The information given in this group will result from the knowledge obtained in phase II in the shape of small leaflets and other information materials to be made according to the best practice, to be given and remembered at scheduled times to the intervention group.

Data collection

The collection of the data will occur in the beginning and end of phase II.

Patient's socio-demographic and clinical characteristics and medication will be registered using the same methodology as described in phase I.

Perception of medication will be evaluated using Portuguese general BMQ, the willingness to be deprescribed will be assessed with two open-questions (the same as phase II), and the quality of life we will assessed with EQ-5D.

For those not knowing how to write, someone of their knowledge, will fill in the open questions.

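### Section 8.3 leaves adjustment for an outcome's own baseline optional, although Phase III plans start and end measurements and allocates only three districts per arm

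*Protocol*

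**What the plan says.** Protocol section 8.3 sets out one list of methods for the whole three-phase study.

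- Qualitative variables: "Associations between qualitative-independent variables will be tested using χ^2 test".
- Quantitative variables compared between groups: "analysis of variance (ANOVA) or Kruskal-Wallis non-parametric test, if normality assumption is not met".
- Adjustment: "ANCOVA may also be used to adjust for potential confounding factors". The confounders are not named.

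In section 4, the data collection paragraph for Phase III reads "The collection of the data will occur in the beginning and end of phase II". It then lists the BMQ, the two open questions on willingness, and EQ-5D.

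The same section sets at least 190 patients per group. It forms one group from Aveiro, Coimbra and Guarda and the other from Castelo Branco, Leiria and Viseu.

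The primary objective is worded in two ways. The synopsis (1.1) has "Willingness to be deprescribed after the intervention". Section 3 speaks of the effect of enablement "in the rise of Willingness to be Deprescribed".

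**The concern.** When an outcome is measured before and after the intervention, its baseline value is usually the most useful covariate available. None of the tests that section 8.3 names outright contains a baseline term when applied to end values. The one method that could is optional and aimed at unspecified confounders. That leaves the decision to adjust, and the choice of covariates, open until the data have been seen.

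This matters more here because whole districts are allocated, three against three. Few allocated units mean larger chance differences between arms at baseline. An end-value comparison without adjustment turns part of such a difference into an apparent effect, or hides a real one. The two wordings of the objective add a second open choice: end value or change. The two analyses can give different answers when the arms differ at the start.

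**Working it through.** **1. Is there a baseline measurement?** The paragraph in section 4 names phase II, but it stands under Phase III and lists EQ-5D, which Phase II does not use. Phase II is cross-sectional with a single collection in June 2018. Phase III is the only reading that fits, and the wording needs correcting.

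**2. The plan's own figure.** Section 8.2 gives 380 patients from a 95% confidence interval and 5% precision. With an assumed proportion of 0.5, n = 1.96² × 0.25 / 0.05² = 384.1, so 385. A finite-population correction gives 380 for a population of about 35,000, but the protocol states no population figure. The 380 is thus reproduced within about 1%. It is a precision figure for one proportion. It implies no effect size or power, so the reference effect in step 5 is mine.

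**3. Chance baseline imbalance.** Inputs from section 4: 190 per arm and three districts per arm, so 190/3 = 63.3 patients per district. The intracluster correlation (ICC) is assumed.

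- Individual randomisation: √(2/190) = 0.103 SD.
- District allocation: √(2/190 × DEFF), with DEFF = 1 + (63.3 − 1) × ICC.

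| Assumed ICC | DEFF | SD of baseline difference |
|---|---|---|
| 0.01 | 1.62 | 0.131 |
| 0.02 | 2.25 | 0.154 |
| 0.05 | 4.12 | 0.208 |

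**4. How much carries over.** Let ρ be the correlation between baseline and end value, assumed 0.3 to 0.7. An unadjusted end-value difference inherits ρ times the baseline difference if the same ρ holds between districts. A one-standard-deviation imbalance then carries 0.3 × 0.131 = 0.04 SD to 0.7 × 0.208 = 0.15 SD.

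A simulation (2,000 trials per scenario, normal data, 190 independent patients per arm, no true effect, assumed baseline difference of 0.2 SD) gave these rejection rates at the 5% level:

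| ρ | ANOVA | Kruskal-Wallis | Baseline ANCOVA |
|---|---|---|---|
| 0.3 | 8.4% | 7.6% | 4.4% |
| 0.5 | 16.6% | 15.7% | 5.4% |
| 0.7 | 26.7% | 25.6% | 4.6% |

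These rates hold only for that assumed imbalance. They are not the overall error rates of the tests.

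**5. Precision, for independent patients only.** Variance relative to an unadjusted end-value comparison is 1 − ρ² for ANCOVA and 2(1 − ρ) for a change score. The reference effect is (1.960 + 0.842) × √(2/190) = 0.287 SD, which the unadjusted comparison detects with 80.0% power.

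| ρ | ANCOVA variance | Change variance | ANCOVA power | Change power |
|---|---|---|---|---|
| 0.3 | 0.91 | 1.40 | 83.6% | 65.8% |
| 0.5 | 0.75 | 1.00 | 89.9% | 80.0% |
| 0.7 | 0.51 | 0.60 | 97.5% | 95.1% |

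**6. The normality switch.** The power simulation was repeated with an assumed ceiling 0.5 SD above the mean, at the same reference effect:

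| ρ | ANOVA | Kruskal-Wallis | Baseline ANCOVA |
|---|---|---|---|
| 0.3 | 72.9% | 74.6% | 75.8% |
| 0.5 | 74.2% | 75.8% | 83.2% |
| 0.7 | 72.8% | 74.6% | 92.0% |

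So non-normality of this kind is no reason to give up baseline adjustment.

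**The case against.** Section 8.3 is a generic list for three phases. It names no Phase III model, it does provide for ANCOVA, and the exact covariates commonly go to a statistical analysis plan. ANOVA on a change score fits both 8.3 and the wording of section 3, and it uses baseline. A reader might infer that the protocol commits Phase III to an analysis that ignores baseline; the text does not go that far. What stands is that it makes adjustment optional and never says which quantity is compared.

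Three other strong readings are not supported:

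- **That the switch to Kruskal-Wallis makes matters worse than ANOVA.** Neither uses baseline when applied to end values, and in the ceiling simulation Kruskal-Wallis did slightly better. Its drawbacks are that it gives no mean difference and cannot adjust. The protocol gives no distribution for EQ-5D, so failure of normality is itself an assumption.
- **That adjustment is worth a given number of extra patients.** Step 5 treats patients as independent. By m × ICC / DEFF, with m = 63.3, districts account for 63.3 × 0.01 / 1.62 = 39% of the variance of an arm mean at ICC 0.01 and 63.3 × 0.05 / 4.12 = 77% at ICC 0.05. The gain therefore depends on the district-level correlation, which is unknown. Willingness comes from two open questions with no defined score, so no ρ can be given for the primary outcome at all.
- **That the synopsis and section 3 define conflicting endpoints.** Under random allocation, differences in end value and in change have the same expectation. They differ in precision and in how chance imbalance affects them, and the section 3 wording may simply mean higher. The texts need aligning, but they are not irreconcilable.

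**Conclusion.** The point holds as a matter of prespecification. Section 8.3 names unadjusted tests and leaves baseline adjustment optional with unnamed covariates, in a trial that plans baseline measurements and allocates six districts.

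The expected chance imbalance is about 0.13 to 0.21 SD against 0.10 SD, if the ICC is 0.01 to 0.05. For independent patients and a scored outcome, ANCOVA variance is 0.91 to 0.51 of the unadjusted variance, if ρ is 0.3 to 0.7. Neither the ICC nor ρ comes from the protocol. The precision figures apply at most to EQ-5D and BMQ, and they do not transfer directly to district allocation. The conclusion also rests on reading the collection times as those of Phase III. Baseline adjustment limits the effect of imbalance but leaves the clustering to be handled separately.

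**What to change.** - **Section 8.3:** replace the permissive sentence with a prespecified Phase III comparison of the end value adjusted for its own baseline. Use ANCOVA or a linear mixed model for EQ-5D and BMQ. Use a baseline-adjusted logistic or ordinal model for willingness, once its coding is defined.
- **Normality:** use that model whatever a normality check shows. Keep Kruskal-Wallis as a sensitivity analysis only.
- **District:** do not enter it as a fixed effect, because district determines arm and the two cannot be separated. If it is included, use a random effect or a cluster-level analysis, with a small-sample correction for six clusters.
- **Endpoint:** state the baseline-adjusted end value in both the synopsis and section 3.
- **Section 4:** correct the collection times to Phase III.

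No new visits or data are needed if Phase III baseline values are collected as read here. The cost is revised wording and a slightly more complex analysis; the small number of districts needs care in the model.

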Perception of medication will be evaluated using Portuguese general BMQ, the willingness to be deprescribed will be assessed with two open-questions (one to assess the facilitators and the other to assess the barriers), and the actual self-medication will be evaluated with an analogic visual scale (0 to 10) about the need to self-medicate and its justification.

For those not knowing how to write or read, someone of their knowledge, will fill in the open questions, with their answers.

In case of less than 5% of answers of the open questions, two patient groups will be invited to make a focus group asserting reasons for accepting deprescribing.

Phase III: impact of enablement of older adults in their willingness to deprescribe and quality of life

Design

Non-pharmacological randomised clinical study, intended to last for six months.

Setting

Primary Care Centres in Portugal will be randomly selected from six Health Centres of Centre of Portugal (Aveiro, Castelo Branco, Coimbra, Guarda, Leiria and Viseu)

Sample size

Will be created two groups with a minimum of 190 patients each (one will be the intervention group and the other the control).

Study procedures

This phase of the study is expected to start in September 2019 and will last for 6 months.

Again, GPs sampling will be made according to existing files and those who accept to participate will recruit their own patients. Patients from previous phases can be enrolled in phase III. Assuming that a GP will be able to include at least 6 patients, a total of 64 GPs has to be enrolled in the study. Enrolled GPs will be instructed to invite all older adult (≥ 65 years) patients attending to the primary care consultation to participate in the study during until obtaining the sample size and being randomized according to the table for study entry. The geographical areas of work, the Districts, will be randomized for entry into exposed and unexposed groups. Those patients willing to participate in the study must give written informed consent and present willingness and ability to comply with the study requirements.

Exclusion criteria: Being acutely unwell in the last three weeks, and refuse to participate.

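### Phase III allocates six whole districts (3 v 3), but section 8.3 tests the groups as if patients were independent, so the stated 5% level is not held

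*Protocol*

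**What the plan says.** In section 4 (Phase III, Study procedures) the protocol states: "The geographical areas of work, the Districts, will be randomized for entry into exposed and unexposed groups". It then lists the groups by district. For the first it says "one of which will be composed from patients from the region of Aveiro, Coimbra and Guarda". The second is made up of Castelo Branco, Leiria and Viseu. Each group is to have at least 190 patients. The sentence just before the district statement describes invited patients as "being randomized according to the table for study entry", which can be read as patient-level randomisation.

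Section 8.3 is the only analysis section. For categorical outcomes it names the chi-square test ("Associations between qualitative-independent variables will be tested using"). For quantitative outcomes: "Comparisons between two or more independent groups regarding a quantitative variable are to be conducted using analysis of variance (ANOVA) or Kruskal-Wallis non-parametric test". On adjustment: "ANCOVA may also be used to adjust for potential confounding factors". On the level: "All tests will be two-sided, considering a significance level of 0.05".

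Section 8.2 derives the 380 patients from a 95% confidence interval and a 5% precision error. The protocol nowhere mentions clustering, an ICC, a design effect, a mixed model or a district-level analysis.

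**The concern.** If whole districts are allocated, the group difference contains the differences between districts as well as any intervention effect. The tests in section 8.3 have no district or GP term. They estimate the standard error from variation between patients and so omit the between-district part. Optional ANCOVA on confounders does not supply it, and a fixed district effect could not be added because each district lies wholly within one group.

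The p-values and confidence intervals would be too optimistic for both Phase III objectives, willingness to be deprescribed (primary) and quality of life (secondary). The error favours a false claim that the enablement intervention works.

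**Working it through.** **Inputs from the protocol.** Six districts, three per group (section 4); 190 patients per group, 380 in total (sections 4 and 8.2); two-sided 0.05 (section 8.3). Mean district size m = 380/6 = 63.3.

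**Assumed.** The district ICC, taken from 0.001 to 0.05; roughly equal district sizes.

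**The plan's own figures.** The single-proportion precision formula gives 1.96² × 0.25 / 0.05² = 384.1, close to the stated 380. It contains no design effect. With ICC = 0 the named tests do have a level of 5%.

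**Level under district allocation.** Design effect DE = 1 + (m − 1) × ICC. True level = 2 × [1 − Φ(1.96/√DE)].

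| ICC | DE | 1.96/√DE | True level | Effective patients per group (190/DE) |
|---|---|---|---|---|
| 0.001 | 1.06 | 1.90 | 5.7% | 179 |
| 0.005 | 1.31 | 1.71 | 8.7% | 145 |
| 0.01 | 1.62 | 1.54 | 12.4% | 117 |
| 0.02 | 2.25 | 1.31 | 19.1% | 85 |
| 0.05 | 4.12 | 0.97 | 33.4% | 46 |

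**Simulation, no true effect, districts of 63 to 64 patients.**

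| Analysis | ICC 0.01 | ICC 0.02 | ICC 0.05 |
|---|---|---|---|
| ANOVA | 12.2% | 19.4% | 33.6% |
| Chi-square, proportion 0.5 | 11.8% | 18.6% | 33.1% |
| Kruskal-Wallis | 11.9% | 19.4% | 33.2% |
| Patient-level ANCOVA on baseline, correlations 0.6 within district and 0.9 between districts | 8.3% | 10.8% | 20.3% |
| Patient-level ANCOVA on baseline, correlations 0.3 and 0.6 | 11.0% | 16.8% | 29.6% |
| Patient-level t test if patients were individually randomised | 5.0% | 5.0% | 4.9% |

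A t test on six district summaries, unadjusted or baseline-adjusted, stayed between 4.7% and 5.6% throughout. Baseline adjustment at patient level therefore reduces the excess when district effects are more stable over time than patients' own values, but does not remove it.

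**Power of a valid analysis.** The protocol gives no effect size. As a benchmark, take the effect that 190 v 190 independent patients would detect with 80% power: d = (1.96 + 0.842) × √(2/190) = 0.287 SD. For an unadjusted t test on six district means, SE = √{(2/3) × [ICC + (1 − ICC)/63.3]}, and power comes from the noncentral t with 4 df (critical value 2.776):

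| ICC | SE | d/SE | Power |
|---|---|---|---|
| 0.001 | 0.106 | 2.72 | 54% |
| 0.005 | 0.118 | 2.45 | 46% |
| 0.01 | 0.131 | 2.20 | 39% |
| 0.02 | 0.154 | 1.87 | 30% |
| 0.05 | 0.208 | 1.38 | 19% |

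With baseline adjustment of the district summaries, power at ICC 0.01, 0.02 and 0.05 is about 65%, 57% and 42% (correlations 0.6/0.9), or 45%, 36% and 23% (0.3/0.6).

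**The case against.** - *The size rests on an ICC that the protocol does not give.* True. Nothing in the document shows that district ICCs reach 0.01, and at 0.001 the excess is trivial. The direction does not depend on the value, though: any positive district ICC raises the level.
- *The phrase about a randomisation table may mean that patients are randomised individually, in which case section 8.3 is sound for the group comparison.* This is the strongest point, and it makes the inflation conditional. But the next sentence names the districts as the randomised units, and the groups are then listed district by district. District allocation is the better supported reading, and under either reading the text needs correcting.
- *Section 8.3 is general text covering all three phases, and an unseen statistical analysis plan might specify a Phase III model.* Possibly. Yet the protocol itself names tests that its own allocation invalidates and offers no other method for Phase III.
- *The remedy costs power even where the inflation is negligible.* This stands. At ICC 0.001 the six-district t test has about 54% power against the 80% benchmark, largely because only 4 df remain. The underlying weakness is allocating six units with a sample size that ignores clustering; changing the analysis reveals this but does not cure it.

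**Conclusion.** The concern holds and should be fixed before the Phase III analysis. Under district allocation as written, the tests in section 8.3 do not deliver the stated two-sided 5% level. The true level is about 12% to 33% for district ICCs of 0.01 to 0.05, and 5.7% to 8.7% for 0.001 to 0.005. These figures assume the ICC and roughly equal district sizes. That the error is towards false positives needs only a positive district ICC. The one reading that avoids it, individual randomisation, contradicts the district sentence and the district lists in section 4.

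**What to change.** First, state one unit of allocation in section 4, Phase III, by reconciling the randomisation-table phrase with the district sentence and the two district lists.

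**If districts are allocated:** state in section 8.3 that Phase III group comparisons are made at district level with small-sample degrees of freedom, and name one method in advance. Either of these would do:
- a two-sided t test on six district summaries (4 df), baseline-adjusted where a baseline value is collected;
- a mixed model with a random district effect and a small-sample df correction.

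The summary should be the district mean or proportion of whatever score is defined for the outcome. Exclude unclustered patient-level tests of the group effect, and word conclusions to match the precision of six districts. Also confirm that the Phase III data-collection sentence, which refers to the beginning and end of Phase II, means Phase III, because baseline adjustment depends on it. A permutation test is no way out: with 20 possible 3 v 3 allocations its smallest two-sided p-value is 2/20 = 0.10.

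**If patients are individually randomised:** correct the district sentences instead. The tests in section 8.3 can then stand for the group comparison.

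**Cost:** text changes only, with no new data. Under district allocation the price is the low power shown above, which comes mainly from having six units. Under individual randomisation the analysis itself loses no power, but GPs recruit their own patients and take part in the intervention, so contamination between groups under one GP could dilute the effect.

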9 SUPPORTING DOCUMENTATION AND OPERATIONAL CONSIDERATIONS

9.1 REGULATORY, ETHICAL, AND STUDY OVERSIGHT CONSIDERATIONS

9.1.1 INFORMED CONSENT PROCESS

9.1.1.1 CONSENT/ASSENT AND OTHER INFORMATIONAL DOCUMENTS PROVIDED TO PARTICIPANTS

Consent forms describing in detail the study intervention, study procedures, and risks are given to the participant and written documentation of informed consent is required prior to starting intervention/administering study intervention.

9.1.1.2 CONSENT PROCEDURES AND DOCUMENTATION

Informed consent is a process that is initiated prior to the individual's agreeing to participate in the study and continues throughout the individual's study participation. Consent forms will be IRB-approved and the participant will be asked to read and review the document. The investigator will explain the research study to the participant and answer any questions that may arise. A verbal explanation will be provided in terms suited to the participant's comprehension of the purposes, procedures, and potential risks of the study and of their rights as research participants. Participants will have the opportunity to carefully review the written consent form and ask questions prior to signing. The participants should have the opportunity to discuss the study with their family or surrogates or think about it prior to agreeing to participate. The participant will sign the informed consent document prior to any procedures being done specifically for the study. Participants must be informed that participation is voluntary and that they may withdraw from the study at any time, without prejudice. A copy of the informed consent document will be given to the participants for their records. The informed consent process will be conducted and documented in the source document (including the date), and the form signed, before the participant undergoes any study-specific procedures. The rights and welfare of the participants will be protected by emphasizing to them that the quality of their medical care will not be adversely affected if they decline to participate in this study.

